## **Randomization**

Participants are randomized in a 1:1 ratio into aerobic-then-resistance exercise group (AR, n=28) and resistance-then-aerobic exercise group (RA, n=28). Randomization is stratified by age and HbA1c ( $\leq$  or  $>$ medians) with a block size of 4.

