## **Exercises intervention program**

Exercise intervention is implemented in the gym room at the Community Health Service Center. The room was equipped with multiple devices for both aerobic and resistance training, which allowed a maximum of six participants to perform exercise at the same time. Room temperature is between 18-22 °C, controlled

by air conditioning. The training program is designed to take place three times a week for a total of eight weeks. Exercise intervention is scheduled for approximately 70 minutes per session (30 minutes of aerobic and 30 minutes of resistance, no break between two types, 5-min of preparation and 5-min relaxation stretching movements before and after each intervention), performed between 8:00 to 11:00 or between 14:00 to 16:30, Monday through Saturday. Exercise sessions starts at least 30 minutes after meals.

The target heart rate during aerobic exercise is set as resting heart rate (HR) + 40%-70% of heart rate reserve (HRR). Participants' HRR was calculated based on their resting HR and maximum heart rate ( $HR_{max}=208-0.7\times age$ ) as  $HR_{max} - HR$ . Heart rate monitors (OH1, Polar Oy, Oulu, Finland) are used during all exercise sessions to track exercise intensity and ensure that it remained within the specified range. Aerobic exercise is performed on bicycle ergometers (Ergoselect 100K, Ergoline GmbH, Bitz, Germany) for a continuous 30 minutes with a progressive intensity of 40%-70% HRR. Resistance level is set according to an adaptive training prior to the first intervention, pedal cadences are 50-60r/min.

Resistance exercise is conducted using a set of equipment (Nanjing Kuanyue Health Technology Co., Ltd, Nanjing, China) including chest press/ row, leg extension/ curl, abdominal/ back, biceps/ triceps, inner/ outer thigh, and push/ pull machines. Prior to conducting the 1 repetition maximum (RM) testing for the major muscles of the upper and lower limbs, all participants receive proper instructions on how to use the equipment. The Brzycki 1-RM prediction equation is used to estimate the 1RM based on the recorded resistance and repetitions. All participants performed resistance exercise with a weight of 60%-80% 1RM. Movements on each machine are repeated 10-12 times per unit for a total of 4 units, with a 30 second break between units. Resistance training involves progressive overload over an 8-week period.

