In all intervention sessions, participants in AR group complete aerobic exercise before starting resistance exercise, while participants in RA group perform two types of exercise in a reversed order. Participants are instructed to maintain their usual lifestyle but refrain from engaging in other forms of regular exercise throughout the intervention period. Prior to enrollment and during the intervention period, weekly dietary guidance on diabetes management is delivered by a dietitian from the Community Health Service Center to minimize the possibility of dietary changes during the intervention.

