### **Statistical analysis plan**

A sample size of 54 participants is considered adequate to achieve 95% power for detecting within-between interactions, using measures taken at pre- and post-intervention time points, based on a medium effect size ( $f = 0.25$ , G\*Power, version 3.0.10). Analyses are carried out following the intention-to-treat principle. The personnel who conduct the analyses are blinded about participants' randomization group. Data are checked for normality by using the Shapiro-Wilk test. Between group comparisons of the outcome variables are

conducted using analysis of covariance (ANCOVA), controlling for the baseline value of the variable of interest, while within-group pre-post-intervention comparisons are performed using paired samples t-tests. Between-group comparisons of non-normally distributed outcome variables are conducted using the Mann-Whitney U test, and within-group comparisons are conducted using the Wilcoxon signed-rank test. Repeated measures analysis of variance (ANOVA) is used to analyze blood glucose levels at various time points during exercise and recovery periods (90 minutes post-exercise), including the main effects of time and group, as well as interaction between time  $\times$  group. Additionally, the change rates of overnight blood glucose levels recorded by CGM on non-exercise days are analyzed for the main effect of group. Between group comparisons of baseline values are analyzed using independent samples t-tests, Mann-Whitney U test, or chi-square test. All tests are two-tailed, P values  $< 0.05$  are considered statistically significant. All analyses are performed using SPSS statistical software version 26 (IBM Corp., Armonk, NY, USA).

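### The time × group test on glucose during exercise cannot by itself show that order matters, because mid-session the arms have done different exercise types

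*Combined protocol and SAP*

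**What the plan says.** The SAP's repeated measures ANOVA is to "analyze blood glucose levels at various time points during exercise and recovery periods (90 minutes post-exercise"). The terms of that model are given as "including the main effects of time and group, as well as interaction between time" and group. The SAP does not list the time points, say which sessions are used, or say whether these readings come from the CGM sensor. It names no follow-up contrast and gives no rule for reading a significant interaction.

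The section on the exercise programme gives the session as "30 minutes of aerobic and 30 minutes of resistance, no break between two types". On the arms it says that "participants in AR group complete aerobic exercise before starting resistance exercise, while participants in RA group perform two types of exercise in a reversed order". The Randomization section puts 28 participants in each arm.

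The sample size statement concerns a different comparison: it refers to interactions "using measures taken at pre- and post-intervention time points, based on a medium effect size". The SAP does not call the acute glucose analysis primary.

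**The concern.** Count minutes from the start of the first exercise type. The arms have done the same exercise only at minute 0 and from minute 60 on. At minute 30 the comparison is 30 minutes of cycling against 30 minutes of weights. That difference would be the same if everyone stopped there and no sequence existed.

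Suppose the two types change glucose at different rates and the total change does not depend on order. The curves then part, are furthest apart at minute 30, and meet again at minute 60. A difference that opens and closes over time is a time × group interaction.

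At stake is the reading of the result. The trial is about exercise sequence, and this is its only stated analysis of the acute glucose response. A significant interaction could be reported as showing that order matters after the same work, when it shows only that the types differ while they are being done.

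**Working it through.** **1. The plan's own figure.** The SAP states N = 54 for 95% power at f = 0.25. For two groups and two measurements, λ = N·m·f²/(1 − ρ). With an assumed pre/post correlation ρ = 0.5 (not stated in the plan), λ = 54 × 2 × 0.0625 / 0.5 = 13.5 on 1 and 52 df, and power is 0.9501. The figure reproduces, but it sizes a pre/post comparison and says nothing about the during-exercise test.

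**2. Exercise completed, by arm** (exercise programme section)

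| Minute | AR | RA | Same content? |
|---|---|---|---|
| 0 | none | none | yes |
| 30 | 30 min aerobic | 30 min resistance | no |
| 60 | both | both | yes |
| 60–150 (recovery) | both | both | yes |

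**3. Size, in closed form.** From the documents: n = 28 per arm, 30 + 30 minutes, 90 minutes of recovery, two-sided 0.05. Assumed: a between-arm difference d(t) rising linearly from 0 to Δ at minute 30 and back to 0 at minute 60, then staying at 0; independent within-person errors with SD σ; readings every 30 minutes (6 points) or every 15 minutes (11 points).

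λ = (n/2) · Σ(d(t) − mean d)² / σ²

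For 6 points and Δ = 1.0, the sum is 1 − 1/6 = 0.833. For 11 points it is 1.5 − 4/11 = 1.136. Both scale with Δ². With σ = 1.0 and 6 points, λ = 14 × 0.833 = 11.67 on 5 and 270 df, and the rejection rate is 74%.

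| Δ (mmol/L) | σ = 0.8 (6 / 11 points) | σ = 1.0 | σ = 1.5 |
|---|---|---|---|
| 0.5 | 32% / 33% | 21% / 21% | 11% / 11% |
| 1.0 | 92% / 95% | 74% / 78% | 37% / 38% |

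**4. Size, by simulation with a Greenhouse–Geisser correction**, so that the excess is not due to non-sphericity.

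| Setting (all assumed) | Δ = 0 | Δ = 0.5 | Δ = 1.0 | Δ = 1.5 |
|---|---|---|---|---|
| Between-person SD 2, within-person SD 0.8–1.5, within-person correlation 0.6 at 30 min, 4 or 8 points | – | 12–48% | 41–99.7% | 87–100% |
| Total SD 2.0, correlation 0.8–0.9, every 15 or 30 min | 4–5% | 21–49% | 84–99.7% | 99.8–100% |

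In the same data, the between-arm test of change from start to end of session rejects at 4–6%. With the ANOVA restricted to minutes 0, 60, 90, 120 and 150, the corrected interaction test rejects at 4.0–4.6% for Δ of 0, 1.0 or 1.5. These near-5% rates follow from setting the difference to zero from minute 60. They show that matched-point tests ignore the mid-session gap, not that order has no effect. The group main effect rejects at 4–9%, because it averages in the mid-session points.

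**5. Is minute 60 a clean comparison?** Only if glucose responds at once. With an assumed first-order lag τ, additive effects and Δ = 1.0, the difference left at minute 60 is Δ(τ/30)(1 − e^(−30/τ))².

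- τ = 10: 0.333 × 0.950² = 0.30 mmol/L.
- τ = 20: 0.667 × 0.777² = 0.40 mmol/L.

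By the end of recovery this is multiplied by e^(−90/τ), which leaves under 0.01 mmol/L in both cases. Averaged over recovery, it is multiplied by (τ/90)(1 − e^(−90/τ)), which leaves 0.03 and 0.09 mmol/L. Recovery readings are therefore the better basis.

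**The case against.** The strongest reply is that nothing is wrong with the test. Order is the only thing randomised, so any difference between the curves, mid-session included, is caused by the assigned order. The SAP promises only to test time, group and their interaction, and the rates above are power to detect a real difference in shape. This stands. A reader might infer that the test is invalid or has an inflated type I error, and the documents do not support that. What the reply does not supply is a way to get from a difference in shape to a net effect of order, and the SAP names no contrast that would do so.

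It is also tempting to say that mid-session readings show type and not order. That goes too far. Between minutes 30 and 60 each arm does its second type after a different first type, so type and order are mixed there. The whole curve also includes recovery.

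Two further replies stand in part. The time points are not given: if the exercise period contributed only its start and end, the unequal-content problem would disappear, apart from any lag at the end of the session. The wording does not say so. And the rates rest on assumed variances, correlations, sampling grids and type differences, so they show what could happen and do not forecast this trial.

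**Conclusion.** The point holds as a limit on interpretation. If mid-session readings enter the model, a significant time × group result cannot by itself show that order matters once the same work is done. That follows from the session structure and the model, and needs no simulation.

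The size depends on inputs outside the documents. Taken together, the calculations give rejection in roughly 10–50% of trials at a 0.5 mmol/L type difference and 35% to over 99% at 1.0 mmol/L, with no difference from minute 60. Significance is therefore not assured whenever the types differ: at 0.5 mmol/L it may well not appear.

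A reader might also infer that the trial's main conclusions are undermined. The documents do not support this. Outcome comparisons before and after the intervention use baseline-adjusted ANCOVA, which this does not touch. The point is a low-cost improvement to one acute-glucose analysis.

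**What to change.** In the SAP, for the acute glucose analysis:

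- List the time points, the sessions used and the source of the glucose readings.
- Prespecify a between-arm comparison, adjusted for pre-exercise glucose, of mean glucose over the 90-minute recovery or of glucose at its end. Choose one as the lead.
- Add end-of-session glucose, adjusted in the same way, as supportive, because it may still carry a lag from the most recent exercise type.
- Keep the whole-curve time × group test as a description of curve shape. State that mid-session differences mix exercise type with order and are not, on their own, evidence of a net order effect.

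The cost is SAP wording. The comparisons use pre-exercise, end-of-session and recovery readings; recovery readings are already part of this analysis, and the time-point list should confirm the other two. The ANCOVA form matches what the SAP already uses for its other outcomes. The downside is that a mid-session difference alone would no longer support a conclusion about sequence.

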## **Continuous glucose monitoring**

Participants undergo a 14-day continuous glucose monitoring (CGM, FreeStyle libre Pro, Abbott Diabetes Care Ltd, Witney, UK) started at two time points: one week before initializing the exercise intervention and at the 8th week of the intervention. An ambulatory glucose monitoring sensor is attached to the posterior aspect of the participants' non-dominant arm, with a guide needle implanted into the subcutaneous tissues. Sensor attachment is manipulated by a research assistant at the study site, between 8:00 to 10:30 on the same day of blood sample collection. Participants do not have access to their own CGM data during the monitoring periods. Following the monitoring period, data are exported and saved from the sensor using scanner of the CGM system by a research assistant at the study site. CGM data collected starting from 00:00 on the second day following the sensor attachment until 00:00 on the day of sensor detachment are included in the analyses.

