## **Assessments of regular glycemic outcomes and covariates**

Baseline information included age, sex, duration of T2D, and medication are obtained by the specialist physician during the recruitment procedure. Prior to the exercise intervention, participants' body mass index (BMI) and blood pressure were measured at the study site. Measurements of participants' fasting plasma glucose, fasting insulin, and hemoglobin A1c (HbA1c) are taken within the week before and after an 8-week exercise intervention. Following an overnight fasting period of  $\geq 8$  hours, 10 ml of venous blood is collected before breakfast (7:00-8:00), and tested by the Laboratory Department of the Community Health Service Center.

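### The combined protocol and SAP names no primary outcome and no multiplicity rule, so at least five unranked between-arm analyses of exercise order share one 0.05 threshold

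*Combined protocol and SAP*

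**What the plan says.** The rule for significance, in the Statistical analysis plan section, is general: "All tests are two-tailed, P values" below 0.05 count as significant. No alpha split, testing order or correction accompanies it, and no outcome anywhere in the document is called primary, secondary or exploratory.

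The sample size is given in the same section: "A sample size of 54 participants is considered adequate to achieve 95% power for detecting within-between interactions". It uses pre and post measurements and a medium effect of f = 0.25. No outcome, standard deviation or pre-post correlation is attached to it.

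The order-related analyses are spread over three sections:

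- **Laboratory outcomes.** "fasting plasma glucose, fasting insulin, and hemoglobin A1c (HbA1c) are taken within the week before and after an 8-week exercise intervention". Arms are compared by ANCOVA adjusted for the baseline value. If the data are not normal, "Between-group comparisons of non-normally distributed outcome variables are conducted using the Mann-Whitney U test".
- **Exercise and recovery glucose.** A repeated-measures ANOVA, "including the main effects of time and group, as well as interaction between time" and group.
- **Overnight CGM.** "the change rates of overnight blood glucose levels recorded by CGM on non-exercise days are analyzed for the main effect of group".
- **Other CGM data.** The Continuous glucose monitoring section says that readings "until 00:00 on the day of sensor detachment are included in the analyses", but lists no summary measures.

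Alongside these, "within-group pre-post-intervention comparisons are performed using paired samples t-tests", with a signed-rank test as the non-normal alternative. They fall under the same threshold and are not labelled descriptive.

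**The concern.** The randomised question is whether aerobic-then-resistance and resistance-then-aerobic exercise differ. Several between-arm tests address it, and the document does not say which one decides it. Followed as written, a P value below 0.05 on any of them could be reported as a significant effect of order, and the chance of at least one such result under no effect is well above 5%.

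A second consequence is that the 95% power belongs to no identifiable endpoint. A reader of a null result on HbA1c, say, could not tell whether the trial was sized for that outcome.

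The within-arm tests add a smaller problem of interpretation. A change within one arm contains the effect of exercise in general, of time and of regression to the mean, so it cannot answer the question of order. The document does not separate these tests from the between-arm ones.

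**Working it through.** **1. Reproducing the planned sample size.** Inputs from the Statistical analysis plan: N = 54, f = 0.25, two measurements, power 95%, two-sided 0.05. Inputs from Randomization: two arms, 1:1. Pre-post correlation r: not stated, so assumed.

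For the within-between interaction, λ = f² × N × 2 / (1 − r), with 1 and N − 2 degrees of freedom. At r = 0.5, λ = 0.0625 × 54 × 2 / 0.5 = 13.5 and power is 95.0%. N = 52 gives 94.2%, so 54 is the smallest even total. At r = 0.3 the same formula gives 86%, and at r = 0.7 above 99%. The planned figure therefore reproduces with r = 0.5, which the document should state.

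**2. Counting the between-arm analyses.** Fasting glucose, fasting insulin and HbA1c (3) + exercise and recovery glucose (1) + overnight CGM change rate (1) = 5. The ANCOVA and Mann-Whitney tests are alternatives for one outcome and are counted once. Within-arm and baseline tests are left out. CGM summary measures are not listed, so five is a minimum.

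**3. Chance of at least one false positive.** With independent tests and all nulls true: 1 − (1 − 0.05)^5 = 1 − 0.774 = 0.226. With correlated tests, take five normal statistics with common correlation c, each two-sided at 0.05. The document gives no correlations, so a range is shown.

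| Assumed correlation c | At least one P < 0.05 |
|---|---|
| 0 | 0.226 |
| 0.3 | 0.209 |
| 0.5 | 0.183 |
| 0.7 | 0.148 |

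**4. What a fix costs in power.** The cost should be computed for the planned ANCOVA, not for the interaction test used in the sample size. Assume equal standard deviations and no baseline imbalance. For two arms and two times, f = 0.25 corresponds to a between-arm difference in change of Δ = 4f = 1.0 SD. Check: (N/4) × Δ² / [2(1 − r)] at r = 0.5 is 13.5 × 1 / 1 = 13.5, the λ of step 1. For ANCOVA, λ = (N/4) × Δ² / (1 − r²), with 1 and N − 3 degrees of freedom. At N = 54:

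- r = 0.5: λ = 13.5 / 0.75 = 18.0
- r = 0.3: λ = 13.5 / 0.91 = 14.8

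If one of the five is primary, four remain. The first Holm step for four secondaries is 0.05 / 4 = 0.0125.

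| r | Power at 0.05 | Power at 0.0125 |
|---|---|---|
| 0.3 | about 96% (0.965) | 89% |
| 0.5 | about 99% | 95% |

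A simulation of the ANCOVA gave 96% and 98% at 0.05, and 88% and 94% at 0.0125, so the formula is close.

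**The case against.** The strongest reply is that the plan already holds the right contrast. It specifies a baseline-adjusted comparison of the arms, sizes the trial on a between-arm interaction, and blinds the analysts to group. It states a conventional threshold, not a rule that any one significant test proves an effect of order. All of this is true. Blinding limits selection by favoured arm, but it does not control the number of tests, and nothing in the document ranks them.

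Four stronger readings are tempting, and the documents do not support them.

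- **That the trial has no primary outcome at all.** The document carries a registration number, and a primary outcome may be declared there. That record was not available, so the point is limited to this document.
- **That the trial is too small.** A reader might infer this from the 86% at r = 0.3. That figure is for the interaction test. Under the planned ANCOVA, power at r = 0.3 is about 96%, and N = 50 would be enough for 95%.
- **That there are six tests, counting group and time × group separately.** The terms come from one ANOVA. In a balanced design under sphericity they are independent, and with several time points the interaction has several degrees of freedom. A six-test calculation with one common correlation does not fit that design.
- **That order will be judged by one arm's paired test being significant and the other's not.** The plan nowhere says so, and reporting within-arm changes beside an ANCOVA is not in itself a fault. Only the missing descriptive label stands.

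The choice between Holm and an exploratory label is a matter of preference; either would do.

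**Conclusion.** The point holds for this document and is worth correcting. With one 0.05 rule, no primary outcome and no multiplicity approach, the chance of at least one false between-arm finding on order is about 15% to 23% over the five identifiable analyses, three to over four times the nominal 5%. This assumes that all five nulls are true, that each analysis acts as a single 5% test, and that the correlations lie between 0 and 0.7. Unlisted CGM measures would push it up; stronger correlation would bring it down.

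The sample-size arithmetic is not at fault: it reproduces at r = 0.5. What is missing is the outcome it applies to and the correlation it assumes. The absence of a primary outcome and of a multiplicity rule is read directly from the text; the error and power figures rest on assumed correlations.

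**What to change.** Amend the Statistical analysis plan section as follows.

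1. Carry over the registered primary outcome, if one exists. If none does, name one outcome and one time point before unblinded results are seen; if they have been seen, label the choice post hoc.
2. Test the primary at two-sided 0.05 with the baseline-adjusted ANCOVA already planned, and tie the sample size to that outcome, stating the assumed pre-post correlation.
3. List the other outcomes, including any CGM summary measures. Label them exploratory, or apply Holm to a short secondary list.
4. State that conclusions about order rest on the between-arm contrasts, and that within-arm tests are descriptive.

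This is wording only and needs no more participants. The primary loses no power. The downside is that fewer results can be called significant. With four secondaries under Holm, first-step ANCOVA power at N = 54 for the same f = 0.25 effect falls from about 99% to 95% at r = 0.5, and from about 96% to 89% at r = 0.3. The exploratory label avoids that loss but gives up confirmatory claims on those outcomes.
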